7.9.1. Analysis of the Exploratory Efficacy Endpoint

The same ANCOVA model specified for the primary endpoint will be used to analyze the endpoints from CPET and continuous CMR measurements that are only assessed once post randomization. Body weight will not be included in the model to analyze CMR parameters. The same MMRM model will be used to analyze the continuous endpoints measured at multiple visits post randomization. CMH test stratified by randomization factors will be used analyze endpoints evaluation proportion of responders or binary outcomes.

Proportion of responders at each week will be summarized. Responders that are defined based on NYHA classification or LVOTs will be assigned after data handling in case there are missing NYHA class or LVOT assessments. Missing NYHA classification or LVOT value will be imputed the same way as that for the secondary endpoints that are based on NYHA classification or LVOT value. Patient will be treated as non-responder if patient's response status can't be determined due to the missing NYHA classification or LVOT assessments (after the imputation above) or clinical visits not performed after the patient early terminates from the study. Proportion of responders will be analyzed using Cochran–Mantel–Haenszel (CMH) test stratified by randomization factors. The p-value and 95% CI will be obtained using exact method. Proportion of patients remaining SRT eligible at Week 24 will be analyzed using logistic model regression model stratified by beta blocker use/non-use adjusting for significant baseline characteristics. The model will include treatment as fixed effect and baseline characteristics as covariates. Covariates measured as continuous will be introduced to the model as continuous variable. Stepwise model selection method will be used based on the default stay or entry level of 0.05 to evaluate significant baseline covariates. Supportive analysis using CMH stratified by randomization factor (beta-blocker use/non-use) will be performed. Another supportive analysis of proportion of patients SRT eligible at each visit will be provided using a repeated measure logistic regression model with treatment, visit, treatment by visit and significant baseline characteristics from the model above. Time to first SRT ineligible in patients who are SRT eligible at baseline will be analyzed using Kaplan-Meier method.

For NT-proBNP and hs-cardiac-TnI, the log transformed proportional change will be analyzed using a MMRM model with log baseline as covariate, treatment group, randomization stratification factors, visit, log baseline by visit and treatment by visit interaction as fixed effects. Log transformed proportional change in Valsalva and resting LVOT will be analyzed using the

same model. Geometric LS Means estimate and ratio of proportional change in NT-proBNP and hs-cardiac-TnI between aficamten vs. placebo, 95% CI of ratio and p-value will be presented. Median and median difference of NT-pro-BNP and hs-cardiac- Tnl between treatment group and 95% confidence of the median difference will be presented at Week 12 and 24. Time to 1 mm ST depression at Week 24 will be analyzed using Cox regression model with treatment, randomization stratification factors as fixed effect. Patients didn't experience 1 mm ST depression will be censored at the end of CPET exercise. Logistic regression model will be fit to LVH strain pattern on ECG for Week 12 and 24, separately. The model will include baseline LVH pattern, stratification factors and treatment. Difference in proportion of patients with no LVH will be estimated and 95% CI for odds ratio (aficamten vs. placebo) and its corresponding p value will be obtained.

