8.2. Efficacy Assessments

8.2.1. Cardiopulmonary Exercise Testing

All patients will undergo CPET with gas-exchange analysis and the methodology will be standardized across all participating sites, as described in the CPET manual. Testing will include continuous ECG monitoring by trained personnel and be performed in an area that is equipped for cardiopulmonary resuscitation. Treadmill is the preferred modality for exercise testing. For CPET laboratories that do not perform treadmill testing, cycle ergometry is an acceptable alternative. Exercise protocols for both modalities will be provided in the CPET manual. Patients

must use the same testing modality for all exercise tests during the trial. Whenever possible, CPET should be administered by the same trial personnel using the same equipment and performed after the other trial procedures on that visit day (including echocardiogram, KCCQ, EQ-5D-5L, CGI, PGI-C, NYHA class, SAQ-7, vital signs, ECG, blood sampling, IP administration). Patients naïve to exercise protocols will be familiarized with the technique during screening.

All CPET testing will be symptom-limited and patients will be strongly encouraged to achieve maximal exertion and an RER ≥ 1.05 . The reason(s) for termination of sub-maximal exercise tests will be documented. A test will be identified as being maximal effort if the RER is ≥ 1.05 .

Patients should not engage in strenuous exercise for 24 hours prior to the CPET, and patients should not exercise at all within 12 hours prior to the test. Patients should fast for at least 4 hours prior to CPET. All regularly scheduled medications should be taken as normal. Patients should avoid taking medications that cause drowsiness within 8 hours prior to the test. Weight should be collected immediately prior to each CPET.

The Week 24 CPET should be performed at approximately the same time of day (eg, morning, mid-day, afternoon) as the baseline CPET at screening, at a consistent time after the last dose of beta-blocker and IP. Whenever possible, patients should perform exercise testing between three and ten hours after taking beta blocking agents.

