 - LVEDV
 - Extracellular volume proportion
 - Late gadolinium enhancement proportion
 - Mitral regurgitation severity
- Time to Maximal ST Segment Depression on CPET ECG
- Time to 1 mm ST depression below Baseline on CPET ECG
- Maximal ST segment depression on resting ECG in mm at Weeks 12 and 24
- Number of patients with new or worsening ST depression during exercise at Week 24
- Change from baseline values in all other summary KCCQ scores (Physical Limitation, Symptom Stability, Symptom Frequency, Symptom Burden, Total Symptom Score, Self-efficacy, Quality of Life, Social Limitation, Overall Summary Score) at Weeks 12 and 24.
- Proportion of patients with LVH with strain pattern (typical+ atypical) on Electrocardiogram (ECG) at Weeks 12 and 24
- Proportion of patients with all LVH (with or without strain) on ECG at Weeks 12 and 24

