3.5.1.4. CPET Assessments

All patients will undergo CPET with gas-exchange analysis and the methodology will be standardized across all sites as specified in the CPET manual. Patients must use the same testing modality for all exercise tests during the trial. CPET are done at baseline and Week 24 post randomization. CPET parameters are listed below. A full list of CPET parameters is specified in the data transfer agreement from core lab.

- Workload
- Exercise Duration
- % of Predicted Oxygen Uptake
- Circulatory Power
- Predicted Oxygen Uptake
- Peak Oxygen Uptake per Kilogram
- Peak RER
- Oxygen Uptake Efficiency Slope
- Ventilatory Efficiency
- Anaerobic Threshold
- Aerobic Efficiency

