7.4. Planned Covariates

Baseline covariates include but are not limited to the stratification factors and baseline measurements. For CPET related endpoints, covariates age, sex, baseline weight will also be evaluated. See [Section 7.7.4](#) for details evaluating covariates effect in the primary endpoint.

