where trtid is assigned as 0 at baseline, 0 for placebo group at Week 24 and 1 for active group at Week 24. &c1 and &c2 are the proportion of patients evaluated in each stratification level among all the patients.

Subgroup analysis for the primary endpoint

```
proc mianalyze parms=mixparms covb(effectvar=rowcol)=mixcovb;  
  class <treatment arm> <beta blocker use> <exercise modality> <subgroup> ;  
  =<base pvo2 > <base weight> <treatment arm> <beta blocker use> <Exercise modality>  
  modeleffects Intercept <base pvo2 > <base weight> <treatment arm> <beta blocker use>  
  <Exercise Modality> <subgroup>*<treatment arm>;  
run;
```

SAS codes to evaluate normality assumption for the primary endpoint

The normality assumptions for the ANCOVA analysis will be assessed by residual illustration. The outpred option in the above code stores residuals which are used to test the assumption of normality. Examination of residuals can be done using the following codes.

```
proc univariate data=work normal;  
var ScaledResid; QQPLOT ScaledResid;  
ods output QQPlot=qqplot;  
run;
```

SAS codes to perform CMH test

```
proc freq data=work;  
  tables <Beta blocker use>*<CPET modality>*<treatment arm>*<response Y/N>/CMH  
  exactcmh;  
  exact riskdiff (column=2) relrisk (column=2) commor.  
Run;  
where response is coded as Y=1, N=0.
```

SAS codes to rank observation

```
proc rank data=work out=rwork nplus1;  
Var chg;  
Ranks rchg;  
Run;
```

SAS code for proportional hazard Cox regression model

```
Proc phreg data=work;  
  Class <treatment arm>(ref=first) ;  
  Model <time>*< censor (1)>= ;  
  Strata <beta blocker use> <CPET modality> ;  
Run;
```

SAS code for stratified logistics regression model

```
Proc phreg data=work;  
  Class <treatment arm>;  
  Model <Response> (event='Y')= <treatment arm> <baseline covariates>/selection=stepwise  
  details;  
  Strata <beta blocker use> ;  
Run;
```

SAS code for EQ-5D-5L Index Value

```
*****  
*SAS syntax code for the computation of index*  
*values with the US TTO value set*  
*****  
  
data WORK.CAT;  
set WORK.CAT;  
  
if mobility eq 1 then disut_mo=0;  
else if mobility eq 2 then disut_mo=0.096;  
else if mobility eq 3 then disut_mo=0.122;  
else if mobility eq 4 then disut_mo=0.237;  
else if mobility eq 5 then disut_mo=0.322;  
  
if selfcare eq 1 then disut_sc=0;  
else if selfcare eq 2 then disut_sc=0.089;  
else if selfcare eq 3 then disut_sc=0.107;  
else if selfcare eq 4 then disut_sc=0.220;  

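### The exploratory Cox model for time to 1 mm ST depression leaves out the screening CPET result of the same measure, giving up some power (about 3 to 10 points at an assumed correlation of 0.5)

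*SAP*

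**What the plan says.** SAP 2.2.3 lists as an exploratory endpoint "Time to 1 mm ST depression below Baseline on CPET ECG". SAP 7.9.1 gives the method: "Time to 1 mm ST depression at Week 24 will be analyzed using Cox regression model with treatment, randomization stratification factors as fixed effect". It adds the censoring rule: "Patients didn't experience 1 mm ST depression will be censored at the end of CPET exercise". The matching block in SAP 11.5 reads "Model <time>*< censor (1)>=" with nothing after the equals sign, and puts beta-blocker use and CPET modality in a STRATA statement.

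On what is available before treatment, SAP 3.5.1.4 says "CPET are done at baseline and Week 24 post randomization", and Protocol 8.2.1 says of each test "Testing will include continuous ECG monitoring by trained personnel". SAP 2.2.3 also plans "Number of patients with new or worsening ST depression during exercise at Week 24", which can only be scored against an earlier exercise test.

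The other models in SAP 7.9.1 carry their own baseline. NT-proBNP, hs-cTnI and the two LVOT gradients have log baseline and its interaction with visit, and the LVH model has the baseline LVH pattern. SAP 7.4 says in general terms: "Baseline covariates include but are not limited to the stratification factors and baseline measurements".

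**The concern.** Whether, and how soon, a patient reaches 1 mm of ST depression is likely to carry over from one exercise test to the next, so the screening result is probably among the better predictors of the Week 24 result. Randomization is stratified only by beta-blocker use and CPET modality. A chance difference between arms in baseline exercise ST depression would therefore pass into the hazard ratio uncorrected, and the test of treatment would be weaker than it could be. The SAP gives no reason for treating this endpoint differently from its neighbours.

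The stakes are small. Under SAP 7.1 exploratory endpoints are assessed at a nominal 0.05 without multiplicity adjustment, and this one is not among the eleven steps of SAP 7.6.

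**Working it through.** **Inputs from the documents.** 270 patients randomized 1:1, 10% without the primary CPET change, difference 1.5 and SD 3.5 mL/kg/min, two-sided 0.05 (SAP 3.3.1). Evaluable patients: 270 × 0.9 = 243, or 121.5 per arm.

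**Inputs that are assumptions.** The event fraction for 1 mm ST depression, the effect size, and the correlation r between the screening and Week 24 tests. The documents give none of these.

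**Step 1: the plan's own figure.** The only stated power is for pVO₂. SE = 3.5 × √(2/121.5) = 0.449; 1.5/0.449 = 3.340; Φ(3.340 − 1.960) = 91.6%. This agrees with the stated figure of more than 90%. There is no stated power for the ST endpoint to reproduce.

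**Step 2: formula guide.** For a continuous outcome, adjusting for a baseline correlated at r multiplies the test statistic by 1/√(1 − r²). At r = 0.5 the factor is 1.155:

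- Unadjusted power 80%: (1.960 + 0.842) × 1.155 − 1.960 = 1.275, so 89.9%, a gain of 9.9 points.
- Unadjusted power 90%: (1.960 + 1.282) × 1.155 − 1.960 = 1.783, so 96.3%, a gain of 6.3 points.

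Starting from 80% unadjusted, the gain is 3.6 points at r = 0.3 and 17.5 at r = 0.7. A censored Cox model need not follow this formula, hence step 3.

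**Step 3: simulated Cox model.** 243 patients, 1:1, censoring at end of exercise, correlated latent times at the two tests, 1,000 trials per cell (Monte Carlo error about 1 point). The adjusted model adds the observed, censored screening time and an indicator of whether 1 mm was reached. Entries are power (%) without → with adjustment, for effects set near 80% and near 90% unadjusted power.

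| r | Control event fraction | Near 80% | Near 90% |
|---|---|---|---|
| 0.3 | 30% | 78.3 → 80.0 | 88.3 → 89.0 |
| 0.3 | 50% | 76.9 → 79.5 | 88.8 → 90.4 |
| 0.3 | 80% | 76.7 → 80.2 | 88.0 → 90.2 |
| 0.5 | 30% | 79.1 → 82.1 | 87.8 → 91.7 |
| 0.5 | 50% | 80.1 → 86.6 | 87.1 → 92.2 |
| 0.5 | 80% | 74.0 → 83.7 | 85.8 → 90.8 |
| 0.7 | 30% | 79.4 → 88.7 | 87.9 → 94.9 |
| 0.7 | 50% | 77.1 → 92.0 | 87.0 → 96.4 |
| 0.7 | 80% | 74.1 → 92.4 | 86.5 → 97.2 |

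The gains run from 0.7 to 3.5 points at r = 0.3, 3.0 to 9.7 at 0.5, and 7.0 to 18.3 at 0.7. When unadjusted power is below 70% at r = 0.5, the gain is about 4 to 12 points. A separate simulation with 25 to 43% events gave about 3, 6 to 8, and 15 points at the three correlations, inside the same ranges.

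**Step 4: where the gain comes from, and its cost.** At r = 0.5 the standard error of the log hazard ratio did not fall on adjustment: 0.249 became 0.252 in one simulation and 0.271 became 0.276 in another. What moved was the estimate, with the log hazard ratio going from −0.64 to −0.71. In the step 3 cells with a 50% control event fraction and about 80% power, the hazard ratio goes from 0.56 to 0.52.

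With no treatment effect, 4,000 trials per cell gave rejection of 4.8 to 5.3% unadjusted, against 5.6 to 6.0% adjusted at r = 0.5 and 6.5 to 6.8% at r = 0.7. A further 12,000 null trials gave 5.1% unadjusted and 5.8% adjusted. In a simulation with 29 to 42% events, correcting for test size reduced the gain at r = 0.5 from 6 to 7 points to about 4 to 5.

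**The case against.** The best case for leaving the plan alone is that treatment plus stratification factors is a valid randomized comparison, on an exploratory endpoint with no power target, and that other analyses in the SAP (the CMH tests, the Kaplan-Meier analysis of SRT ineligibility) also carry no baseline covariate. SAP 7.4 already names baseline measurements as covariates. All of that is correct, but SAP 7.4 does not name this model, and a programmer would follow the specific text and code, which omit the term.

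Several stronger readings are tempting, and the documents do not support them:

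- **A single firm loss of power.** Event rate, effect, correlation and censoring pattern are all assumed. The simulations also treat end of exercise as unrelated to ST onset, which is doubtful when exercise capacity is what the drug is meant to change. Only a range can be given.
- **A less precise hazard ratio.** Step 4 shows that the standard error does not shrink. The power comes from a conditional hazard ratio further from 1.
- **A change with no downside.** The target of estimation changes, and the adjusted Wald test is mildly liberal.
- **A timed screening onset that is certainly in hand.** The Protocol describes ECG monitoring. The CPET parameters listed in SAP 3.5.1.4 include no ST variable and defer to a data transfer agreement. Scoring new or worsening depression needs baseline presence or severity, not an onset time. Nor does the endpoint wording say whether its baseline is the resting tracing or the study baseline of SAP 5.6.

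One technical objection to the remedy also stands in part. Using onset time for some patients and exercise duration for others puts two quantities in one covariate. The accompanying indicator separates the two groups in level but still gives them a common slope.

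**Conclusion.** The concern holds as a minor point of analysis choice. The Cox model and its code omit the screening result, the neighbouring models do not, and no reason is given. Subject to the assumptions listed in the working, the power given up is about 1 to 4 points at r = 0.3, 3 to 10 at r = 0.5 and 7 to 18 at r = 0.7. With few events (30% in controls) at r = 0.5, the loss is mostly toward the lower end of its range. Part of each figure is the adjusted test's slightly raised rejection rate and not real sensitivity.

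A reader might infer that the planned analysis is biased, or that the trial's stated power is in doubt. Neither follows: the unadjusted test keeps its level, the primary model already adjusts for baseline pVO₂ and body weight, and nothing in the testing sequence depends on this endpoint.

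The Cox code is a separate and plainer defect. As printed, it does not include treatment, and its stratified form is not the fixed-effect model that the text describes.

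**What to change.** In SAP 7.9.1, keep treatment and the stratification factors and add:

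1. An indicator of whether 1 mm ST depression was reached on the screening CPET.
2. Where the core laboratory supplies onset time, the screening time to 1 mm, or screening exercise duration if 1 mm was not reached. If onset time is not supplied, use the indicator alone.

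State that the adjusted hazard ratio is conditional on these terms, and keep the unadjusted model as a sensitivity analysis. Say which baseline the 1 mm is measured from.

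In SAP 11.5, put treatment and the new terms in the MODEL statement, and make the code and text agree on whether the stratification factors are strata or fixed effects.

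The cost is a few sentences and two covariates, with no new patient assessments. The change should be made before unblinding. The downsides are the changed target, a standard error that does not shrink, and null rejection of about 5.5 to 6% at r = 0.5 and slightly higher at 0.7.

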8. SAFETY AND TOLERABILITY

Safety and tolerability analyses will be based on the Safety Analysis Set. Safety data will be analyzed descriptively and tabulated by treatment groups.

8.1. Overall Summary of Tolerability

Overall summary of tolerability will include the following:

- Number of patients treated
- Number of patients with TEAEs
- Number of patients with treatment-emergent serious adverse events (TESAEs)
- Number of patients with TEAEs leading to premature treatment discontinuation
- Number of patients with at least one TEAE related to the study drug
- Patients with at least one moderate or severe TEAE
- Patients with at least one severe TEAE
- Number of Deaths

Summary of number and percent of patients with each AE category will be provided by treatment group and dose level at AE onset. Summaries of the number of events will also be provided.

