6.6. Dose Modifications

6.6.1. Scheduled Dose Titrations

Patients randomized to CK-3773274 may receive up to four escalating doses of IP over the initial 6 weeks of the trial as outlined below in [Table 4](#). Patients receiving CK-3773274 start at a dose of 5 mg once daily (Dose 1) and may escalate through doses of 10, 15, and 20 mg once daily if they continue to meet the escalation criteria or will stop at their current dose when escalation criteria are not met.

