6.6.1.1. Week 2 Visit

After randomization each patient will receive Dose 1 once daily for two weeks. At the Week 2 visit, the patient will have an echocardiogram 2 hours following administration of their dose of IP. Patients will up-titrate to Dose 2 if the following conditions are met on echocardiography:

- Post-Valsalva LVOT-G ≥ 30 mmHg, and the biplane LVEF $\geq 55\%$

Otherwise, the patient will remain on Dose 1.

If LVEF is $< 50\%$ at Week 2, the IWRS will assign the patient to placebo.

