3. STUDY DESIGN

3.1. Summary of Study Design

This is a Phase 3, randomized, placebo-controlled, double-blind, multi-center trial in patients with symptomatic oHCM. Approximately 270 eligible patients will be randomized in a 1:1 ratio to receive CK-3773274 or placebo. Randomization will be stratified by use of beta-blockers (yes or no) and CPET exercise modality (treadmill or bicycle) and implemented in the Interactive Web Response System (IWRS). A cap on the number of patients taking beta-blockers and will not exceed approximately 70% of total enrollment. The number of patients taking disopyramide will be capped at approximately 10% of total enrollment. The number of patients with persistent atrial fibrillation at screening will also be capped at approximately 15%, and the number of patients using the bicycle CPET exercise modality will be capped at approximately 50% as well.

Investigational product (IP) will be administered orally once daily with or without food. During the initial six weeks of the treatment period, IP doses will be individually titrated at Weeks 2, 4, and 6 using echocardiography. Dose escalation at Weeks 2, 4, and 6 will occur only if a patient has a post-Valsalva LVOT-G ≥ 30 mmHg and a biplane LVEF $\geq 55\%$. Echocardiograms will be performed at each subsequent visit during the trial and the dose down titrated if necessary. The primary endpoint of pVO₂ will be measured by CPET at screening and at end of treatment (Week 24). If applicable, patients will continue taking background HCM medications consistent with regional clinical practice guidelines during the trial.

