8.2. Adverse Event Preferred Term and Body/Organ System Summary Tables

8.2.1. Summaries of Adverse Event Incidence Rates for All Subjects

All AE terms will be coded using MedDRA. TEAEs and TESAEs will be summarized by primary SOC and PT, and also by severity (mild, moderate and severe) and relationship to study drug (related and not related). For a TEAE reported more than once from a patient, the TEAE will be counted only once in the SOC or PT category using the most severe occurrence or closer relationship to the study drug. All AEs will be listed.

The following subsets of TEAEs will be summarized by SOC and PT:

- All TEAEs
- TEAEs related to study drug
- TEAEs leading to early discontinuation of study drug
- TESAEs

A summary of all TEAEs by PT will be provided. AE summaries will be sorted by descending order of SOC in aficamten group and descending order of preferred term within the SOC. TEAE and TESAE summary of $\geq 5\%$ and $\geq 2\%$, respectively will be provided based on incidence rate in either aficamten or placebo group. Summary of TEAEs by maximum severity will display number and percentage of AEs with maximum severity being mild, moderate, or severe within

each SOC and PT. All TEAE summary will also be provided by dose level. Summary of number of events will be provided for all TEAE summary.

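### Adverse event percentages by dose level at onset take no account of unequal time at each dose, so they can show a spurious dose trend

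*SAP*

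**What the plan says.** SAP 8.1 plans for each adverse event (AE) category: "Summary of number and percent of patients with each AE category will be provided by treatment group and dose level at AE onset". It adds that "Summaries of the number of events will also be provided". SAP 8.2.1 says of the coded events: "All TEAE summary will also be provided by dose level". Neither section gives the denominator of a by-dose percentage, patient-time at the dose, or an exposure-adjusted rate.

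Exposure is planned only in total (SAP 8.3.1). The number of patients at each dose by visit is a separate table (SAP 8.3.2) that is not linked to the AE percentages. The whole safety analysis is descriptive: "Safety data will be analyzed descriptively and tabulated by treatment groups".

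On titration, Protocol 6.6.1 says that patients on active drug "may receive up to four escalating doses of IP over the initial 6 weeks of the trial". Protocol 6.6.1.1 sets the first step: "After randomization each patient will receive Dose 1 once daily for two weeks". Further steps are possible only at Weeks 4 and 6, and Protocol 6.6.2 rules out escalation after Week 6. Patients "will stop at their current dose when escalation criteria are not met". Treatment lasts 24 weeks (Protocol 4.1.4).

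**The concern.** A table of AE percentages with one column per dose will be read as dose-response, whatever the SAP calls it. The chance that a patient has at least one event in a column grows with the time spent in that column, and here that time is set by the titration scheme. Every patient on active drug passes through 5 mg, many perhaps for only two weeks, while anyone who reaches 20 mg and is not reduced stays there for most of the trial. Columns with such different time at risk cannot be compared as crude percentages. A reader could see a dose effect that is not there, or miss an early hazard at a low dose because few weeks were spent at it. The SAP also names no denominator, so even the direction of the distortion cannot be told in advance.

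**Working it through.** The documents give no figure for AEs by dose, so there is no stated result to reproduce.

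**Inputs from the documents.** Steps at Weeks 2, 4 and 6 only; 24 weeks of treatment; patients who stop escalating remain at their dose.

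**Assumptions, not in the documents.** The overall AE incidence, the split of final doses, and the same hazard at every dose. No reductions or dropouts; patients who escalate do so at consecutive visits from Week 2; the 28-day period after the last dose is left out.

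**Step 1: nominal weeks at each dose.**

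| Final dose | 5 mg | 10 mg | 15 mg | 20 mg |
|---|---|---|---|---|
| 5 mg | 24 | – | – | – |
| 10 mg | 2 | 22 | – | – |
| 15 mg | 2 | 2 | 20 | – |
| 20 mg | 2 | 2 | 2 | 18 |

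**Step 2: chance of at least one event in d weeks.** With 60% overall incidence, h = −ln(1 − 0.60)/24 = 0.0382 per week and P(d) = 1 − exp(−h·d). This gives P(2) = 7.35%, P(18) = 49.7%, P(20) = 53.4%, P(22) = 56.8% and P(24) = 60.0%.

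**Step 3: even split of final doses (25% each), patients ever at the dose as denominator.**

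- 5 mg: 0.25 × 60.0 + 0.75 × 7.35 = 20.5%
- 10 mg: (1/3) × 56.8 + (2/3) × 7.35 = 23.8%
- 15 mg: (1/2) × 53.4 + (1/2) × 7.35 = 30.4%
- 20 mg: 49.7%

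The trend is upward although the hazard is the same at every dose.

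**Step 4: most patients stay at 5 mg.** With 75% staying, the 5 mg column is 0.75 × 60.0 + 0.25 × 7.35 = 46.8%, against 49.7% at 20 mg. The two columns are equal when the share staying is (49.7 − 7.35)/(60.0 − 7.35) = 80%.

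**Step 5: whole arm as denominator.** Multiply the Step 3 values by the share who ever reach each dose (100, 75, 50 and 25%). The result is 20.5, 17.9, 15.2 and 12.4%, so the trend reverses.

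**Step 6: events clustered early.** Take a hazard of 0.08·exp(−t/4) per week at Week t and assumed final-dose shares of 10, 20, 30 and 40%, with patients ever at the dose as denominator. The columns become 13.4, 9.6, 7.3 and 6.8%. For example, the cumulative hazard over Weeks 0–2 is 0.32 × (1 − e^(−0.5)) = 0.126, or 11.8%. Over Weeks 0–24 it is 0.32 × (1 − e^(−6)) = 0.319, or 27.3%. The 5 mg column is then 0.1 × 27.3 + 0.9 × 11.8 = 13.4%. Again the direction is reversed with no dose effect.

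**Step 7: person-time.** Under the constant hazard of Step 2, first events divided by time at risk at the dose give 3.82 per 100 patient-weeks (× 52 = 199 per 100 patient-years) in every column, for any dose mix. Time at risk must stop at the patient's first event at that dose. If all time at the dose is counted instead, the 20 mg pathway gives 7.35/2 = 3.7 per 100 patient-weeks at 5 mg and 49.7/18 = 2.8 at 20 mg, which is not flat.

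**The case against.** The safety analysis is descriptive, no dose-trend test of AEs is planned, and events of special interest and low ejection fraction are tabulated by treatment group (SAP 8.2.2). Total exposure and dose by visit are reported, and all AEs are listed. The table shells are in separate documents and might state denominators. All of this stands, and it keeps the point minor. It does not remove it, because none of those displays gives the time at risk behind a by-dose percentage.

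SAP 8.2.1 says only by dose level, not at onset. SAP 5.2 speaks generally of the highest dose level administered, and SAP 5.7.8 defines a dose group from the Week 8 assignment. If 8.2.1 follows either of these, each patient sits in one column for the whole period and the argument above does not apply to that table. This also stands.

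A reader might infer a stronger claim: that the table will show a rising dose trend when there is none, with 7% at 5 mg against 50% at 20 mg (Step 2, 2 against 18 weeks). The documents do not support it. Two weeks at 5 mg is the minimum, since patients who do not escalate can stay there for 24. Eighteen weeks is the shortest nominal final-dose period, not the longest. The pair of 7% and 50% describes one patient's path to 20 mg, not two columns of the table. Nothing in the documents shows that a true dose effect is absent.

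Person-time rates are also not a cure. Dose follows echocardiographic response and calendar time, so with early-clustered events a rate table would make 5 mg look worst.

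**Conclusion.** The point holds in a limited form. By-dose AE percentages under SAP 8.1 are not adjusted for time at dose, and the titration rules make that time unequal by design, so the table can show a spurious dose trend. Under a constant hazard with 60% overall incidence, an assumed even split of final doses and patients ever at the dose as denominator, the distortion is about 20% against 50%. It shrinks to 47% against 50% if three quarters stay at 5 mg, and it changes sign under a whole-arm denominator or early clustering. The incidence, dose mix and hazard shape are all assumptions; only the weeks at each dose come from the protocol. The point extends to SAP 8.2.1 only if dose level there means dose at onset. The randomized comparison of arms is not affected.

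**What to change.** In SAP 8.1, and in 8.2.1 if dose level there means dose at onset:

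- Say in 8.2.1 which definition of dose level applies.
- Use patients ever treated at that dose as the denominator of each by-dose percentage.
- Next to the counts, show patient-years at that dose and patients with a first event at that dose per 100 patient-years at risk, with time at risk ending at that first event.
- State which column receives onsets in the 28 days after the last dose, during an interruption, or after a switch from active drug to placebo.
- Add a footnote that dose was assigned by response and calendar time, not randomized, so the by-dose rates are descriptive.

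Crude counts and percentages can stay. The cost is slightly busier tables and one derived exposure variable. Dosing dates and interruptions are already recorded on the case report form (Protocol 6.4), and the dose assigned by the interactive web response system is already to be summarized (SAP 8.3.2), so no new data are needed. What remains after the change is confounding by calendar time and by who is titrated, which the footnote discloses but does not remove.
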